**Is the use of prophylactic NPWT after cesarean in obese women cost-effective?**

Hypothesis: Prophylactic NPWT will be a cost-effective intervention for the prevention of surgical site infections after cesarean in obese women.

#### **3.2. Design and Rationale**

This is a pragmatic multicenter randomized controlled trial. We chose a randomized controlled trial, the 'gold standard' of clinical research design, with the goal of obtaining the highest quality evidence to inform clinical practice. The broad inclusion criteria and evaluation of effects of typical use of prophylactic NPWT make this a pragmatic trial. The multicenter design and inclusion of both academic and community hospitals in two regions of the U.S. with high rates of obesity increase generalizability and direct application of the findings. We will follow the Consolidated Standards of Reporting Trials (CONSORT) guidelines in the conduct and reporting of this trial. Analysis will follow the intention-to-treat principle. By random allocation, patients will receive either prophylactic NPWT or

standard wound care after cesarean delivery. The remainder of perioperative care will be similar for both arms including the administration of standard preoperative antibiotics within 60 minutes prior to skin incision, skin preparation with chlorhexidine alcohol or povidone-iodine solution, and clipping (rather than shaving) of hair as needed prior to incision.

### **3.3. Eligibility Criteria**

#### **3.3.1. Inclusion Criteria**

- Gestational age  $\geq$ 23 weeks
- Pre-pregnancy BMI  $\geq$  30 Kg/m^2 (based on BMI at first prenatal visit, but BMI at delivery will also be collected)
- Undergoing scheduled or unscheduled cesarean delivery

#### **3.3.2. Exclusion Criteria**

- Patient unwilling or unable to provide consent
- Non-availability for postoperative follow up
- Contraindication to NPWT applicable to women undergoing cesarean
  - Pre-existing infection around incision site
  - Bleeding disorder
  - Therapeutic anticoagulation
  - Allergy to any component of the dressing including silver, silicone and adhesive tape
  - Prior irradiated skin

#### **4. Study Procedures**

##### **4.1. The Prevena™ Incision Management System (Peel & Place)**

The Prevena™ Incision Management System incorporates all of the functional elements of NPWT that are necessary for management of closed surgical incisions. The system has the added advantages of being simple in concept and having an anatomically adaptable peel-and-place dressing which is uniquely designed to be skin-friendly. The dressing is easy to apply and use in the operating room (OR) by the surgeon, study staff or surgical staff. The system may also transition from the OR to the hospital and/or outpatient setting for use by multiple care takers.

**Figure 1:** The Prevena™ Incision Management System (Peel & Place)

The Prevena Incision Management System consists of the following components:

- The Prevena™/ Prevena PLUS™ Incision Management System that is applied over clean sutured or stapled incisions in a simple peel-and-place process and applies continuous negative pressure at 125 mmHg through the dressing to the incision site. The Prevena™

Incision Management System accommodates incisions up to 20 cm in length and the Prevena

PLUS™ Incision Management System accommodates incisions up to 35 cm in length.

- The dressing has a built-in pressure indicator that when compressed indicates that the negative pressure in the system is between -75mmHg to -125mmHg. A raised pressure indicator button indicates that the negative pressure is less than 75mmHg.
- A polyurethane coated, polyester fabric interface layer with 0.019% ionic silver wicks fluid from the skin surface. The silver is not intended to treat infection but only to reduce bacterial colonization within the fabric.
- The polyurethane foam bolster that covers the interface layer has a pore size of 400-600 microns and a violet colorant; the foam manifolds negative pressure to the incision site.
- A polyurethane film with acrylic adhesive provides adhesion of the dressing to the skin surrounding the incision. A polyurethane shell encapsulates the foam bolster and interface layer, providing a closed system.
- The unit is battery powered for seven days, lightweight, easily portable and designed for single patient use.
- The Prevena™ 45mL canister or the Prevena PLUS™ 150mL canister for collection of incision exudate.
- Prevena Patch Strips, which may be used to help seal leaks around the dressing
- All patient-contact materials are free of latex and DEHP [Di (2ethylhexyl) phthalate].

#### **4.2. Provider Training on Use of NPWT Device**

All research staff and clinicians (labor & delivery and postpartum nurses, OR technicians, physicians) involved in the study will receive formal training on how to place and remove the prophylactic NPWT device.

- Providers will have to demonstrate proficiency and receive certification by a KCI Representative in order to be part of the study

- Content of the training
  - Placement of the dressing over the wound
    - The dressing will be placed centrally over the wound to reduce the chance of wound fluid coming into contact with the port
    - Placement of the dressing so that the port should be uppermost from the wound and placed over intact skin
    - The dressing should be applied so that the border of the dressing is not creased.
    - Insertion of batteries into the pump
    - Connecting the pump to the dressing by twisting together the tubing connectors
    - Application of fixation strips around 4 sides of the dressing
    - Activation of the device to initiate negative pressure
    - Troubleshooting if negative pressure is not achieved
    - Inspection of dressing and indications for dressing change
  - Patients instructions on pump use
    - Disconnection of the pump for showering
    - Not to submerge dressing in water
    - Wiping the pump clean with a damp cloth using soapy water
    - When to notify the nurse or physician: all pump lights are off (pump is off), if amber light is flashing (indicating a leak), or if all lights are illuminated (indicating a pump failure)

#### **4.3. Screening**

Study personnel at each clinical site will screen and consent patients under the direction of the site PI. Patients will be enrolled at the time of admission for delivery or anytime thereafter prior to cesarean. Each center will have the flexibility to use an approach that is most efficient and suitable for their system to screen and consent patients. Medical records of all potential patients admitted for

delivery will be reviewed and those who satisfy inclusion and exclusion criteria will be approached and written informed consent obtained. A screening log will be used to track all patients approached for the study.

#### **4.4. Randomization**

Women will only be randomized once the decision is made to do a cesarean. A confidential web-based randomization sequence will be prepared by using blocks of variable sizes, stratified by study site, BMI category (30-39.9 and  $\geq 40$  kg/m^2) and scheduled/non-labor versus unscheduled/labor cesareans. The randomization sequence will be maintained centrally by the study statistician. The patient's group assignment will be revealed once basic information including confirmation of the inclusion criteria are submitted online.

#### **4.5. Procedures**

##### *Schedule of Events*

	Enrollment	PP Day 2-7 or Day of Discharge	1-2 weeks Postpartum	Post-Op Day 30 (+/- 2 days)	4-6 weeks Postpartum
Eligibility and Randomization	X				
Interview: Maternal Demographic Characteristics	X				
Skin Swabs/Adipose Tissue Biopsies	X				
Chart abstraction: Prenatal Records		X			
Chart abstraction: Fetal/Neonatal outcomes		X			
Patient Satisfaction Survey		X			
AE/SAE Form		X	X	X	X
Chart abstraction: Outcome Assessment		X	X	X	X
Phone Call/Follow Up Survey		X		X	
Chart abstraction: Post Partum Form					X

##### *Preoperative care*

Routine preoperative cesarean care at each center will be given to patients by their clinical providers. These procedures are similar and all study sites have agreed on basic standardization of SSIs prevention strategies as well as diagnosis and treatment (**Table 2**).

Standardized preoperative procedures include:

- Clipping of hair at site of incision immediately prior cesarean as needed
- Preoperative antibiotics within 60 minutes prior to incision. Typical preoperative antibiotic used is 2-3 g of cefazolin. Penicillin-allergic patients will receive gentamicin and clindamycin. Patients with chorioamnionitis will receive ampicillin, gentamicin, and clindamycin.
- Skin preparation with chlorhexidine-alcohol or povidone-iodine solution with 3-minutes of drying time prior to draping.
- Adherence to these procedures will be recorded and monitored.

*Intraoperative care*

- Choice of incision will be left to the surgeon. The typical incision for a cesarean is a Pfannenstiel (low transverse) skin incision, although body habitus (particularly in obese women) and prior surgeries may dictate the use of a high transverse skin incision above the pannus or a vertical midline skin incision
- The preferred uterine incision will be low transverse, unless intraoperative findings such as dense adhesions or poorly developed lower uterine segment necessitate a classical or high transverse incision
- Closure of the subcutaneous layer if  $\geq 2$  cm
- The preferred skin closure at the participating centers is subcuticular suture. However, type of incision, scar tissue, and patient preference may play a role in the decision to use staples

**Table 2:** Routine infection prevention practices at each study site

	Washington University in St. Louis	University of Alabama at Birmingham	Ochsner Medical Center	Mercy Hospital in St. Louis	Indiana University
Hair clipping	Clipping immediate preop if needed	Clipping immediate preop if needed	Clipping immediate preop if needed	Clipping immediate preop if needed	Clipping immediate preop if needed
Skin Prep	Chlorhexidine-alcohol; iodine-alcohol if allergic to chlorhexidine	Povidone-iodine + Chlorhexidine-alcohol; chlorhexidine gluconate alone for urgent cases	Chlorhexidine for non-urgent cases; betadine for urgent	Betadine-alcohol, chlorhexidine-alcohol for betadine allergy	Chlorhexidine-alcohol for non-urgent cases; betadine for urgent
Antibiotics	Administer Preoperatively Cefazolin: 2g if >80kg, 3 g for >160 kg. If laboring Azithromycin is added. If cephalosporin allergy: gentamicin 2 mg/kg + 900 mg clindamycin.	Administer Preoperatively Cefazolin: 2g if >80kg, 3 g for >160 kg. If laboring Azithromycin is added. If cephalosporin allergy: gentamicin 2 mg/kg + 900 mg clindamycin	Administer Preoperatively Cefazolin: 2g if >80kg, 3 g for >160 kg. If laboring Azithromycin is added. If cephalosporin allergy: gentamicin 2 mg/kg + 900 mg clindamycin	Administer Preoperatively Cefazolin: 2g if >80kg, 3 g for >160 kg. If laboring Azithromycin is added. If cephalosporin allergy: gentamicin 2 mg/kg + 900 mg clindamycin	Administer Preoperatively Cefazolin: 2g if >80kg, 3 g for >160 kg. If laboring Azithromycin is added. If cephalosporin allergy: gentamicin 2 mg/kg + 900 mg clindamycin
Delivery of placenta	Spontaneous	Spontaneous	Manual	Spontaneous	Spontaneous
Subcutaneous layer	Closure if >2cm	Closure if >2cm	Closure if >2cm	Closure if >2cm	Closure if >2cm
Skin closure	Subcuticular suture	Subcuticular suture	Most subcuticular suture; rare staples	Most subcuticular suture; rare staples	Most subcuticular suture; rare staples

Standard wound dressing	Honeycomb dressing stays in place for 24 hours	Honeycomb dressing stays in place for 48 hours	Abdominal pressure dressing x24 hours	Abdominal pressure dressing x24 hours	Abdominal pressure dressing x 24 hours
-------------------------	--	--	---------------------------------------	---------------------------------------	--

- As this is a large pragmatic trial, and many factors play a role in operative decisions, the operative procedures used will be recorded and the impact of these variations on the effectiveness of prophylactic NPWT will be assessed in secondary analyses.

[figure not shown]
#### *Postoperative care*

- Patients will be monitored daily while in the hospital
- Removal of standard surgical dressing at approximately 24 hours in patients randomized to standard dressing
- We will plan to remove the negative pressure wound therapy dressing on postoperative day #4 or day of discharge in patients randomized to prophylactic NPWT with Prevena™/Prevena PLUS™. However, patients who remain hospitalized will have the device on for up to 7 days. Therefore, the minimum duration of therapy will be 2-4 days with an anticipated average of duration of approximately 5 days.
- Replacement of any dressing that is saturated
- If a patient develops infection with the NPWT device in place the device will be removed and the patient given standard SSI therapy as outlined below
- Patients will be educated about the signs and symptoms of infection and other study outcomes and encouraged to call their provider
- Research staff will monitor subjects' inpatient course for signs and symptoms of SSI
- Management of surgical site infections will follow the Practice Guidelines of the Infectious Diseases Society of America
- All patients will sign a medical record release which will be faxed to any hospitals or physician's office to obtain records for review

- All clinical sites will follow policies to routinely send specimens for culture and sensitivity from all accessible infections such as wound/skin infections or drained abscesses in order to identify individual infectious agents and their antibiotic susceptibilities. Outcomes pertaining to microbial resistance will be obtained through subject chart abstraction.

The following infant data will be collected after delivery: Gender, weight, well baby, special care nursery or NICU, APGAR scores, umbilical cord blood gas results, neonatal outcomes and any complications will be collected.

**Figure 2: Algorithm for the management and treatment of surgical site infections (SSIs)**

Dressing changes  
No antibiotics

Dressing changes  
Antibiotics\*

\*Choice of antibiotics will be based on infection severity and local bacteria resistance patterns by the subject's clinical care provider.

#### **4.6. Follow Up**

- We will use active surveillance by research staff to ascertain surgical site infections.
- Research staff will follow-up with the research participant on the day of discharge or within 48 hours (postpartum day 2-7) to assess for adverse events, assess the participant's pain and obtain their satisfaction with their dressing.
- Research staff will call subjects on approximately postoperative day 30 ( $\pm 2$  days). They will ask the patient standardized questions regarding wound complications. If the patient reports a hospital, clinic, or ER visit not associated with the study centers, the staff will obtain the name of the medical facility and request the records.
- The EQ-5D-3L quality of life questionnaire will be administered at the 30-day call.
- Typically, patients will have routine follow-up with their provider scheduled at 1-2 weeks and 4-6 weeks post-partum.
- We will obtain medical records from each of those clinic visits as well as records of unscheduled visits (to any hospital clinic or ER) to ascertain study outcomes

#### **4.7. Withdrawals**

Patients who withdraw from the study after randomization will be excluded from further follow-up. However outcomes ascertained up until the time of withdrawal will be reported in the intent-to-treat analysis.

#### **4.8. Outcome Measures**

##### **4.8.1 Primary Outcome**

Superficial or deep surgical site infections as defined according to the CDC's National Healthcare Safety Network criteria. Diagnosis will be made by the treating physician and reviewed and validated centrally by the PI against the *CDC's National Healthcare Safety Network Definitions of Surgical Site Infections* and blinded to intervention group

A **superficial incisional (or wound) SSI** must meet the following criteria: Infection occurs within 30 days after the operative procedure AND involves only skin and subcutaneous tissue of the incision AND patient has at least one of the following: i) purulent drainage from the superficial incision; ii) organisms isolated from an aseptically obtained culture of fluid or tissue from the superficial incision; iii) at least one of the following signs or symptoms of infection: pain or tenderness, localized swelling, redness, or heat, and superficial incision is deliberately opened by surgeon, and is culture-positive or not cultured (a culture-negative finding does not meet this criterion); iv) diagnosis of superficial incisional SSI by the surgeon or attending physician.

A **deep incisional (or wound) SSI** must meet the following criteria: Infection occurs within 30 days after the operative procedure AND involves deep soft tissues (e.g., fascial and muscle layers) of the incision AND patient has at least one of the following: i) purulent drainage from the deep incision but not from the organ/space component of the surgical site; ii) a deep incision spontaneously dehisces or is deliberately opened by a surgeon and is culture-positive or not cultured when the patient has at least one of the following signs or symptoms: fever ( $>38^{\circ}\text{C}$ ), or localized pain or tenderness (a culture-negative finding does not meet this criterion); iii) an abscess or other evidence of infection involving the deep incision is found on direct examination, during reoperation, or by histopathologic or radiologic examination; iv) diagnosis of a deep incisional SSI by a surgeon or attending physician.

#### **4.8.2. Secondary Outcomes**

[figure not shown]
- Individual components of the primary outcome (superficial or deep SSI)
- Organ space SSI (endometritis)
- Other individual wound complications: dehiscence  $\geq 2$  cm, hematoma, seroma, erythema

- Composite of any wound complications
- Patient pain and satisfaction scores at discharge and postoperative day 30
- Patient satisfaction with aesthetic appearance (scale of 0 - 10) at postoperative day 30
- Healthcare resource utilization: physician office or ED visits, antibiotics for SSI, hospital readmission for SSIs, home health for SSI, wound clinic for SSI
- Adverse events: skin blistering, allergic reaction, wound bleeding

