#### *Cost-Effectiveness Analysis*

The economic analysis will be led by [name], MPP, MPH, PhD, an MFM Specialist and Health Economist with extensive experience in cost-effectiveness analysis. We will adhere closely to the guidelines for economic analysis accompanying clinical trials set forth by the international Task Force on Good Research Practices on RCT Cost-Effectiveness Analysis. The primary perspective of this economic evaluation will be societal, but we will also examine the patient and health care payer perspectives. This analysis will follow the intention-to-treat principle. The time horizon for the analysis will be the 30-day follow-up period of the trial, but we will include costs for treatment of SSIs beyond 30 days. Costs and effects will not be discounted because the time horizon for the analysis is short.

**Costs:** Direct medical costs will be the primary measure, but indirect costs may be considered if feasible. Direct medical costs will include the cost of implementing prophylactic NPWT or standard dressing (e.g., device or dressing cost, treatment of side effects), and medical care for SSI (e.g., hospital costs, emergency room, outpatient services, wound care supplies, and medications). Indirect costs will include cost of traveling for outpatient visits and lost productivity from being absent from work or usual activity. Secondary data sources will be used as much as possible to reduce the burden of data collection for economic analysis. Unit costs for inpatient and outpatient services, outpatient procedures, laboratory tests, and office visits will be estimated by using charges adjusted for cost-to-charge ratios. The unit cost of medications will be derived from average wholesale prices. Unit costs for study patients' time will be based on the average national wage rate.

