**Effectiveness:** The effectiveness measures will be rate of SSI and QALYs. We will calculate QALYs by applying utility weights (1=perfect health, 0=death) to various health states values derived from the EuroQol five dimensions questionnaire (**EQ-5D**). The EQ-5D is a standardized instrument for measuring generic health status. The health status measured with EQ-5D-3L is used for estimating preference weight for that health status, then by combining the weight with time, QALYs can be computed. We will administer the EQ-5D to patients at the 30-day follow-up phone call. Once the data have been collected a scoring function can be used to assign a value (i.e., EQ-5D™ index score) to self-reported health states from a set of U.S.-generated value set (preference weights).

EQ-5D is one of the most commonly used generic health status measurement, and its good validity and reliability have been reported in various health conditions. The EQ-5D-3L questionnaire is made up for two components; health state description and evaluation. In the description part, health status is measured in terms of five dimensions (5D); *mobility, self-care, usual activities, pain/discomfort, and anxiety/depression*. Mobility dimension asks about the person's walking ability. Self-care dimension asks about the ability to wash or dress by oneself, and usual activities dimension measures performance in "work, study, housework, family or leisure activities". In the pain/discomfort

dimension, it asks how much pain or discomfort they have, and in the anxiety/depression dimension, it asks how anxious or depressed they are. The respondents self-rate their level of severity for each dimension using a three-level (3L) scale: *having no problems, having some or moderate problems, being unable to do/having extreme problems*. In the evaluation part, the respondents evaluate their overall health status using the visual analogue scale (EQ-VAS) which ranges from 0 (the worst health you can imagine) to 100 (the best imaginable health state).

**Cost-effectiveness:** The measures of cost-effectiveness of prophylactic NPWT will be incremental cost per case of SSI prevented and incremental cost per QALY. They will be calculated as follows.

Incremental cost per case of SSI prevented:

$(\text{Mean Cost}_{\text{Prophylactic NPWT}} - \text{Mean Cost}_{\text{standard care}}) \div (\text{Mean SSI Rate}_{\text{Prophylactic NPWT}} - \text{Mean SSI Rate}_{\text{standard care}})$

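### Direct medical costs and four of the resource-use items cover SSI care but not care for non-infected dehiscence, hematoma or seroma, so the incremental cost can be biased in a direction not known in advance

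*Combined protocol and SAP*

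**What the plan says.** Section 4.8.2 defines the resource-use outcome in one bullet. It opens with "Healthcare resource utilization: physician office or ED visits, antibiotics for SSI" and continues with "hospital readmission for SSIs, home health for SSI, wound clinic for SSI". Four items (antibiotics, readmission, home health, wound clinic) are tied to SSI. Physician office and ED visits are not.

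The same section lists non-SSI complications as outcomes in their own right: "Other individual wound complications: dehiscence" of 2 cm or more, hematoma, seroma and erythema, plus a composite of any wound complication. Adverse events are a separate bullet: blistering, allergic reaction and wound bleeding.

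Section 6.2.2 (Cost-Effectiveness Analysis) takes a societal primary perspective. It gives direct medical costs two components. The first is implementing the dressing, with examples that run "e.g., device or dressing cost, treatment of side effects), and medical care for SSI". The second is "medical care for SSI (e.g., hospital costs, emergency room, outpatient services, wound care supplies, and medications". Costs after day 30 are included only for SSI treatment. Indirect costs (travel, lost productivity) are to be considered if feasible and are not tied to SSI.

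For QALYs, section 6.2.2 says: "The EQ-5D is a standardized instrument for measuring generic health status". It is given once, at the 30-day call.

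**The concern.** Non-infected dehiscence, hematoma and seroma can lead to the same contacts as an SSI: readmission, wound clinic and home nursing. The protocol also gives reasons to expect NPWT to change them. Section 2.1.1 describes fluid and hematoma collecting in the subcutaneous dead space, and mechanical stress promoting dehiscence. Section 2.1.2 credits NPWT with less edema and exudate, lower lateral and shear stress, and better apposition of the wound edges. If NPWT changes how often these events occur, their cost differs by arm and does not cancel from the incremental cost.

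Both cost-effectiveness ratios use that incremental cost. Cost per SSI prevented is affected through its numerator. Cost per QALY has a further problem: its numerator is built around SSI, while its denominator comes from an instrument that is not restricted to SSI. Secondary Aim 2 rests on these ratios.

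A smaller point concerns attribution. Section 4.8.1 provides central review of the SSI diagnosis, blinded to group. Nothing describes a similar review of whether a given readmission, antibiotic course or wound-clinic contact was for SSI.

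**Working it through.** The plan states no figure for this point, so there is none to reproduce. The check is a comparison of text followed by an illustration of size.

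**Step 1. What is counted for a woman with non-infected dehiscence, hematoma or seroma**

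| Contact or cost | Resource-use outcome (4.8.2) | Cost (6.2.2) |
|---|---|---|
| Office or ED visit | Counted | No named direct-cost component |
| Antibiotics, readmission, home health, wound clinic | Not counted | No named direct-cost component |
| Treatment after day 30 | Not addressed separately | Named for SSI only |
| Travel, lost productivity | Not listed | Indirect cost, if feasible, no SSI limit |

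The sensitivity analyses in section 6.2.2 give as examples the SSI rate, the risk reduction, the device cost and healthcare cost. None is stated to add non-SSI wound care.

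**Step 2. Inputs**

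- From the documents: SSI 10% versus 7%, a difference of 0.03 (section 6.1.1); $500 per Prevena unit (section 2.3); threshold $100,000 per QALY (section 6.2.2).
- Assumed, because the documents give no values: non-SSI wound complications in 2-8% of controls; a 30% relative change with NPWT, as planned for SSI; $500-$5,000 per case; a utility loss of 0.1-0.3 over 30 days per SSI.

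**Step 3. Omitted cost per woman** = control rate x relative change x cost per case

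- Low: 0.02 x 0.30 = 0.006; 0.006 x $500 = $3.
- High: 0.08 x 0.30 = 0.024; 0.024 x $5,000 = $120.
- As a share of the $500 device: 3/500 = 0.6% to 120/500 = 24%.
- Per SSI prevented: $3/0.03 = $100 to $120/0.03 = $4,000. The device alone gives $500/0.03 = $16,667, before SSI savings and the unstated cost of the standard dressing.

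If NPWT reduces these complications, the plan overstates the incremental cost by this amount. If NPWT increases them by the same proportion, it understates the cost by the same amount. With no effect, nothing changes.

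**Step 4. Scale against the QALY gain**

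- Gain from 3 fewer SSIs per 100 = 0.03 x (0.1 to 0.3) x 30/365 = 0.00025 to 0.00074 QALY.
- At $100,000 per QALY this is worth about $25 to $74, so the omitted $3-$120 is of comparable order. This comparison leaves out the device cost.

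**Step 5. Does the verdict against the threshold change?** Take the assumptions most favourable to NPWT, $5,000 per SSI and no offset for the standard dressing.

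- Plan's costing: $500 - 0.03 x $5,000 = $350; $350/0.00074 = about $473,000 per QALY.
- Also crediting the maximum omitted saving: $350 - $120 = $230; $230/0.00074 = about $311,000.
- Also crediting a QALY gain for the non-SSI cases, 0.024 x 0.3 x 30/365 = 0.00059: $230/(0.00074 + 0.00059) = about $173,000.

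All three exceed $100,000.

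**The case against.** The strongest defence is that the cost list is not worded as exhaustive. Section 6.2.2 says what direct costs will include, leaves side effects undefined (wound bleeding may overlap with hematoma), and section 5.1 promises complete cost data. The Manual of Operations may say more. This weakens the point without removing it. The examples sit inside two named components, neither of which is wound care other than for SSI, and an analyst following the text would leave that care out. Whether to add it should not be settled after results are seen.

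Some of the care is already counted. Under section 4.8.1 a deep incision that dehisces spontaneously can meet the deep SSI definition, and a physician's diagnosis also suffices. Section 2.1.1 treats fluid and hematoma as a source of infection, so part of their cost arises through SSI. This stands: the gap is the non-infected remainder, and the assumed 2-8% is not reduced for uncertainty about the overlap. SSI-focused costing is also a natural match for cost per SSI prevented, though that ratio still needs the full cost difference under a societal perspective.

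A reader might infer three stronger things that the documents do not support:

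- That all resource use depends on an SSI label. Office and ED visits and the indirect costs do not.
- That QALYs capture every wound complication. The EQ-5D is given only at day 30, with no baseline or earlier measurement described, so a complication that resolved earlier may leave no trace.
- That attribution is wholly unblinded. The SSI diagnosis has central review blinded to group.

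**Conclusion.** The point holds in a limited form. As written, direct medical costs and four of the resource-use items leave out care for non-infected dehiscence, hematoma and seroma. The protocol's own rationale gives reasons to expect NPWT to affect these events, and the primary perspective is societal. The incremental cost is biased to the extent that NPWT changes them, with a sign that cannot be known in advance.

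The size rests wholly on assumptions: $3-$120 per woman for the ranges given, against a $500 device. A reader might go further and infer that the cost-effectiveness conclusion would be reversed. That is not shown, since the ratio stays above $100,000 per QALY in the check above. The check depends on assumed unit costs too, so it does not prove that a reversal is impossible. The primary outcome is unaffected. The change should be made because it concerns a stated secondary aim and is cheap to settle in advance.

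**What to change.** - **Section 4.8.2:** count antibiotics, readmission, home health and wound clinic for any wound complication (SSI, dehiscence, hematoma, seroma) or dressing-related adverse event. Keep the SSI-only count as a sub-item.
- **Section 6.2.2:** widen the second direct-cost component from SSI care to care for SSI and any other wound complication, at least for cost per QALY. Add SSI-only costs and all-cause 30-day costs as sensitivity analyses.

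The cost is a wording change and some extra coding. Section 4.6 already obtains routine clinic records "as well as records of unscheduled visits (to any hospital clinic or ER) to ascertain study outcomes", and section 5.4 obtains authorization for emergency room, office and readmission records. Home-health records are not named there and may need extra abstraction. Cost estimates will be somewhat more variable.
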